7.3 Safety Objective

To demonstrate the safety of BMS-986036 in adults with NASH and stage 3 liver fibrosis throughout the course of the study, including BMD and immunogenicity.

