8.5.3.7 Adverse Events of Special Interest

The sponsor has developed a list of AEs of Special Interest for the BMS-986036 program based on the known biologic class effects, the mechanism of action, and clinical study data. These will include the following:

- Injection site reactions
- Gastrointestinal events
 - Diarrhea, frequent bowel movements, nausea, vomiting, abdominal pain
- Bone-related events
 - Osteoporosis, osteopenia, bone and joint injuries, fractures (except tooth fracture), endocrine abnormalities of gonadal function not elsewhere classified (NEC),

hyperparathyroid disorders, hypoparathyroid disorders, parathyroid disorders NEC, parathyroid analyses, metabolic bone disorders, vitamin D abnormal, vitamin D decreased, vitamin D deficiency, and miscellaneous events related to bone density

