8.5.3.8 Bone Safety by DXA

Potential effects of BMS-986036 on BMD will be evaluated by DXA scans of the hip (including femoral neck) and spine that will be performed during the Screening Period and at the Week 48 Visit (or ET, if applicable) as indicated in the Schedule of Activities ([Section 1](#)). Participants will return for a follow-up DXA assessment 6 months (1 month is defined as 4 calendar weeks) after the Week 52/PTFU Visit. DXA may be performed within a window of ± 7 days of the scheduled Week 48 (or ET, if applicable) Visit and within a window of ± 14 days of the scheduled 6-month follow-up visit. DXA scans will be evaluated by central reading. Acquisition guidelines, instructions on calibration and the handling and submission of DXA scans are included in the Imaging Laboratory Manual. Note that at least one of the requested anatomic sites (hip [including femoral neck] or spine) must be evaluable for participants to be eligible for the study (See [Section 8.3.2](#)).

For participants prematurely discontinuing study medication DXA scans should be conducted at the ET Visit only if the participant has completed at least the Week 16 Visit. If a participant has not completed at least Week 16, the follow-up DXA scan at 6 months after PTFU Visit should also not be performed.

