4.3.6 Bone Mineral Density Testing (BMD)

BMD as measured by DXA at Week 48 (or ET, if applicable), and 6 months (1 month is defined as 4 calendar weeks) after the Week 52/PTFU Visit, following will be summarized.

- Absolute and change from baseline values

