6.2.5 Bone Mineral Density Testing (BMD)

BMD data will be summarized by visit, treatment group, and pooled BMS-986036. In rare circumstances where the number of evaluable lumbar spine segments changes over time for bone mineral density results, only participants with the same number and same segments as their baseline assessment will be included in change from baseline summaries of lumbar spine values. In addition, only participants with at least 2 evaluable lumbar spine segments at baseline will be included in the summary of the baseline time point. All bone mineral density results will be listed. Once available, the quality control (QC)-corrected values of BMD and t- and z-scores will be analyzed.

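### The lumbar spine BMD change summary drops participants whose evaluable segments differ from baseline; using the segments evaluable at both scans would keep those with at least two in common

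*SAP*

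**What the plan says.** BMD is part of the safety objective. Protocol 7.3 aims to show safety "throughout the course of the study, including BMD and immunogenicity". Protocol 8.5.3.8 adds that "Potential effects of BMS-986036 on BMD will be evaluated by DXA scans of the hip (including femoral neck) and spine", at Screening, at Week 48 (or early termination) and 6 months after the Week 52/post-treatment visit. SAP 4.3.6 plans "Absolute and change from baseline values" for BMD, and SAP 6.2.5 summarizes them by visit, by treatment group and for the pooled active arms.

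SAP 6.2.5 has two special rules for the lumbar spine:

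- Change from baseline: if the count of readable vertebrae differs between a participant's scans, which the SAP describes as rare, the spine summary is restricted. The wording is "only participants with the same number and same segments as their baseline assessment will be included in change from baseline summaries".
- Baseline: "only participants with at least 2 evaluable lumbar spine segments at baseline will be included in the summary of the baseline time point".

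The section ends its treatment of affected participants with "All bone mineral density results will be listed". It does not say why a segment might stop or start being evaluable, or whether exclusion applies to one visit or to all. It plans no recalculation on the segments that remain, no count of exclusions by arm and no sensitivity summary.

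**The concern.** The rule has a sound purpose: a spine value averaged over one set of vertebrae is not comparable with a value averaged over another. The weakness is in how it gets there. It removes the participant, and does so on the strength of the post-baseline scan. If segments become non-evaluable for reasons linked to what the drug does to bone, the people left in the change summary are a selected group.

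This matters more here than in a trial with no bone question. Protocol 6.1.1 reports decreases in bone mass, mineralization and strength in animals, and Protocol 8.5.3.7 makes fractures and osteoporosis adverse events of special interest.

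There is also a smaller mismatch. The two-segment minimum is written for the baseline row only, so the baseline, post-baseline and change rows can rest on different participants for a reason other than missing scans.

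**Working it through.** **No figure to reproduce.** The documents give no exclusion rate, expected BMD change, standard deviation or precision for BMD. The first two steps are reasoning from the text; the third is illustration only.

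**Step 1: can an affected scan exist and be left out?** Protocol 8.3.9.1 stops study medication after a major fracture. Protocol 8.5.3.8 still calls for a scan at early termination if Week 16 was completed, and again at the 6-month follow-up. So a participant with a fracture can have post-baseline scans. If the evaluable segments then differ from baseline, SAP 6.2.5 removes that participant from the spine change summary. That a fracture makes a segment non-evaluable is an inference; the documents do not say so.

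**Step 2: the two-segment rule.** Take a participant with one evaluable segment at baseline and the same one at Week 48. Read literally, this person is out of the baseline row (fewer than 2 segments) but in the change row (same number, same segments).

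**Step 3: how large could the effect be?** Let *q* be the share of an arm that is excluded.

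reported mean − mean of all = *q* × (mean of retained − mean of excluded)

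Inputs: about 49 per arm (Protocol 6.2). Assumed, not from the documents: retained mean −1%; 1 to 5 excluded; excluded mean −3% to −8%. Percentages are used only to give a scale.

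| Excluded of 49 | Excluded mean | Mean of all 49 | Loss understated by |
|---|---|---|---|
| 1 | −3% | (48×(−1) + 1×(−3))/49 = −1.04% | 0.04 points |
| 1 | −8% | (48×(−1) + 1×(−8))/49 = −1.14% | 0.14 points |
| 3 | −3% | (46×(−1) + 3×(−3))/49 = −1.12% | 0.12 points |
| 3 | −8% | (46×(−1) + 3×(−8))/49 = −1.43% | 0.43 points |
| 5 | −3% | (44×(−1) + 5×(−3))/49 = −1.20% | 0.20 points |
| 5 | −8% | (44×(−1) + 5×(−8))/49 = −1.71% | 0.71 points |

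For the pooled active group (3×49 = 147), 1 excluded at −3% gives (1/147)×2 = 0.01 points, and 5 at −8% give (5/147)×7 = 0.24 points.

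The sign can reverse. With 2 of 49 excluded who gained 3%, the mean of all is (47×(−1) + 2×3)/49 = −0.84%, so the reported −1.00% overstates loss by 0.16 points. If the excluded participants resemble those kept, the difference is zero.

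**The case against.** The strongest reply is that this is an ordinary comparability rule for an event the SAP expects rarely, in a descriptive summary with no test. It touches one output. Hip and femoral neck DXA are outside it, absolute spine values by visit are not subject to matching, every BMD result is listed, and fractures are tabulated as adverse events of special interest. Screening also removes some high-risk people: Protocol 8.3.2 excludes a T-score of −2.5 or less from age 40 and any fracture within 8 weeks before or during Screening. Protocol 6.3.2.4 reports no effect on BMD after 12 or 16 weeks of dosing. Nothing points to many incident vertebral fractures.

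Most of that stands, and it is why the point is minor. Three qualifications remain:

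- SAP 8.4 limits treatment-emergent events to 30 days after the last dose, and Protocol 8.5.3.1 ends nonserious event collection at Week 52/post-treatment follow-up. A vertebral change first seen on the 6-month scan would generally fall outside the event tables.
- Absolute means without matching can mix different vertebrae, which is the problem the rule was written to avoid.
- Listings keep the data but do not compare arms.

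A reader might infer that the rule can only hide bone loss. The documents do not support that. They give no cause for a segment change, and a change over time can also mean a segment becoming evaluable. Excluded participants could have gained BMD, or could be on placebo, in which case dropping their losses would make the drug look worse. Nor is spine BMD the only quantitative bone information: hip BMD is measured, and Protocol 8.5.2 allows bone biomarkers.

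It is also fair to say that the remedy is partial. A segment lost at follow-up still drops out of the comparison, and participants with fewer than two common segments are still only listed. It keeps more people in; it does not end all dependence on the later scan.

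**Conclusion.** The point holds as a low-severity, cheap improvement. Inclusion in the lumbar spine change summary depends on a post-baseline finding that may be related to bone change, and the SAP neither reports how often this happens by arm nor recovers the usable data. The sign and size of any bias cannot be derived from the documents. The 0.04 to 0.71 points per arm rest wholly on the assumed exclusion counts and changes, and the effect is near zero if exclusions are very few or unrelated to bone. Given the SAP's expectation of rarity and the outputs that remain, the impact is probably small. To read the rule as concealing drug-related fractures would go beyond the text, because no passage links fracture to a non-evaluable segment.

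**What to change.** Amend SAP 6.2.5 as follows:

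1. For each participant and visit, compute lumbar spine BMD at baseline and at that visit over the segments evaluable at both scans, requiring at least 2, and take the change from that pair. Make this the main summary or, if segment-level values are limited, a sensitivity summary beside the planned one. Working visit by visit also settles whether exclusion applies to one visit or to all.
2. Apply the two-segment minimum to the baseline, post-baseline and change rows alike.
3. Tabulate by arm the number of participants whose evaluable segments changed, with the central reader's reason.
4. List participants with fewer than 2 common segments.

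The cost is a few sentences of SAP text and some programming. The existing rule already needs the identity of the evaluable segments. The change also needs segment-level BMD from the central reading, which is assumed to be obtainable because the imaging manual is not among the documents. Baseline is re-derived for a few participants, and any T- or z-scores for them would need values specific to the common segments. If segment-level values cannot be had, items 2 and 3 can still be done.

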6.2.6 Immunogenicity

The definitions, summaries and listings described below apply to statistical analysis for serum anti-BMS-986036 and serum anti-FGF21 antibodies.

In participants that experience immunogenicity, neutralizing activity and exposure-efficacy relationship will be assessed for evidence of a clinical impact on safety and efficacy. All participants will have samples collected for immunogenicity at Day 1 and each subsequent visit through the Week 52/PTFU Visit and at Long-Term Immunogenicity Follow-Up Visits after the Week 52/PTFU Visit).

A positive BMS-986036-induced immunogenicity response is defined as:

1. a missing baseline immunogenicity measurement and a positive laboratory reported immunogenicity response post-baseline
2. a negative laboratory reported baseline immunogenicity response and a positive laboratory reported immunogenicity response post-baseline
3. a positive laboratory reported baseline immunogenicity response and a positive laboratory reported immunogenicity response post-baseline that has a titer value at least 4-fold greater than the baseline titer value

A persistently positive BMS-986036-induced immunogenicity response is defined as post-dose positive results at 2 or more consecutive time-points, where the first and last positive result are at least 16 weeks apart.

Immunogenicity results will be summarized as anti-drug antibody (ADA) negative or ADA positive including persistent positive per treatment group in the safety population. The post-baseline evaluable participants and any neutralizing results will also be included in this summary. All ADA results will be listed.

6.3 Pharmacokinetics

Sponsor: Bristol-Myers Squibb

Protocol no: MB130-068

Pharmacokinetic (PK) profiling of BMS-986036 will be performed on all participants based upon trough sampling prior to dosing at each visit. [REDACTED]

6.3.1 Serum Concentrations

Trough BMS-986036 serum concentrations (in all participants at all visits) [REDACTED]

[REDACTED] will be summarized by treatment and visit for both C-term and Total BMS-986036.

Serum concentrations below LLOQ will be set to missing in the computation of mean concentration values. Descriptive statistics (n, mean, standard deviation (SD), geometric mean, % coefficient variation (CV), median, min, and max) will be used to summarize the serum concentrations at each scheduled time point.

[figure not shown]
Linear and semi-logarithmic plots of the geometric mean serum concentrations + SD versus scheduled sampling times, overlaid by treatment will be provided for trough concentrations. [REDACTED]

[REDACTED] These plots will show study visit and will include a reference line for LLOQ on all plots with just one analyte. The plots will match the summary table results with the exception for time points with no values >LLOQ. For plotting presentation purposes, for time points with no values >LLOQ a value of one-half LLOQ will be used to plot that time point and a corresponding footnote will be added to indicate which time points were affected. All individual subject serum concentration data will be listed.

In addition, individual participant plots of trough concentrations will be presented for all participants and all scheduled time points among the PK population, with C-terminal Intact and total BMS-986036 concentrations on the same plot. [REDACTED]

Sponsor: Bristol-Myers Squibb

Protocol no: MB130-068

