6.1.2 Clinical Studies

In the first-in-human study (**Study MB130001**), BMS-986036 was administered by subcutaneous (SC) injection in single and multiple doses for up to 14 days to 72 obese, nondiabetic, healthy adult volunteers.¹⁶ C-terminal intact BMS-986036, the active polypeptide, displayed a half-life of approximately 20 - 24 hours and demonstrated a generally linear PK with 2-fold to 3-fold accumulation following QD dosing. Following single dose administration in the range of 1 mg to 60 mg, the drug was slowly absorbed from the SC injection site (abdomen) into the systemic circulation, with median time to maximum concentration ranging from 24 to 33 hours. Following a single weekly dose of 21 mg, the time to maximum concentration was like that of single doses. BMS-986036 in doses of up to 30 mg QD for up to 14 days was well tolerated and safe; adverse events (AEs) were mild and showed no dose-ordered trends. In the multiple-dosing panels, BMS-986036 increased adiponectin levels in a dose-dependent fashion. Adiponectin increased by 41.7% in the BMS-986036 30 mg QD group; in contrast, it decreased by 28.5% in the placebo group. Adiponectin has been shown to inhibit hepatic stellate cell proliferation and hepatic fibrosis in vitro,¹⁷ and higher levels of adiponectin have been shown to correlate with improvements in fibrosis, as well as steatosis and inflammation.¹⁸ It is therefore likely that an increase in adiponectin in response to BMS-986036 would have beneficial anti-steatotic, anti-inflammatory, and anti-fibrotic effects in NASH patients. BMS-986036 also improved insulin sensitivity, promoted favorable lipid changes (decreased TGs, apolipoprotein B, and LDL cholesterol), and reduced body weight compared to placebo.

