7.4 Pharmacokinetic Objectives

- To determine trough concentrations of BMS-986036 in all participants

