8.4.2 Study Medication Administration

Participants should be instructed to make every effort to administer study medication on the same day each week at approximately the same time of day. Each weekly administration will consist of 2 SC injections.

On Day 1 and at the Week 4, 8, 12, 16, 20, 24, 32, and 40 Visits, study medication will be self-administered by the participant or administered by their designee at the study site as part of the participant's scheduled study visits. At those visits, study medication dosing should be held until all study-related assessments, including participant questionnaires, vital signs, ECG, AE evaluation, physical examinations, and laboratory sample collection (including trough [predose] PK) have been completed. [REDACTED]

[REDACTED] If a study visit occurs on a day that is not a planned dosing day, the participant should continue to administer the medication on the planned dosing day; all study-related assessments will continue to be performed at the planned study visit (in-clinic administration of study drug would not occur). [REDACTED]

[REDACTED]

Study medication is blinded and is supplied in a pre-filled syringe. Each participant will be dispensed a treatment kit containing 2 smaller boxes (for each weekly administration). Each smaller box will contain 1 pre-filled syringe of the medication. Both syringes will be administered in the abdominal area at different locations per training guidelines. Study medication will be assigned by the IRT system.

Guidance and training on administration should be given to the participant (or caregiver, if applicable) prior to the first administration. At a minimum, the first administration should be done by the participant under the supervision of qualified site personnel. Training may be repeated as necessary at any study visit at the discretion of the investigator to maintain treatment compliance. When injections are administered at the site during study visits, site staff may observe the injection to ensure proper technique is being employed. Participants will be required to capture the date, time, and location of each injection on the supplied study medication administration card.

Specific instructions for study medication administration as well as training materials for participants (or caregivers, if applicable) are in the Pharmacy Manual.

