8.4.6.3 Missed Doses

If a participant misses a dose according to the protocol-outlined schedule, the participant (or caregiver, as applicable) should administer the dose as soon as possible and continue on the original schedule with the exception that 2 doses of medication should not be administered less than 48 hours apart.

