8.5.5 Pharmacokinetics

8.5.5.1 All Participants

Serum concentrations of BMS-986036 will be derived from trough (predose) blood samples collected from each participant before the administration of BMS-986036 dosing at each visit. Participants will be instructed to not administer study medication on the days of clinic visits until the trough PK sample has been collected.

[figure not shown]

[figure not shown]
Table 9 Timing of Pharmacokinetic and Electrocardiogram Assessments

[figure not shown]
Study Day	Event	Time Postdose (sample window)	Pharmacokinetic Sample	Electrocardiogram
Assessments Associated with the Day 1 Visit				
Day 1 (Day of Week 1 dose)	Predose	0 h	X	X
Day 1	Dose			
Day 8 (Day of Week 2 dose)	Predose	0 h	X	
Day 8	Dose			
Assessments Associated with the Week 24 Visit				
Day 169 (Day of Week 25 dose)	Predose	0 h	X	X
Day 169	Dose			
Day 176 (Day of Week 26 dose)	Predose	0 h	X	
Day 176	Dose			

[figure not shown]
Pharmacokinetic samples should be taken after the electrocardiogram assessments are performed at times where both pharmacokinetic samples and electrocardiograms are to be collected.

Day 1 is defined as the day of administration of the first dose of study medication.

BMS-986036 concentrations will be evaluated by a central laboratory. Further details of sample collection, processing, submission and storage are provided in the Study Laboratory Manual.

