8.3 Visit Windows

Visit windows as defined in the protocol are closely monitored by clinical monitors. A protocol deviation will be documented if assessments were recorded outside the visit windows, but the assessment is recorded in the clinical database at the planned visit. For longitudinal summaries of data, assessment recorded at the planned visits in the clinical database are included and displayed in tables with visit based structure.

If there are multiple records within the same visit window, then the value in the visit window closest to the day of the planned visit is selected.

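### SAP 6.3.1, as visibly written, reports PK samples from every visit as trough with no check on time since the last dose, so off-day samples can bias the trough summaries

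*SAP*

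**What the plan says.** The PK objective in Protocol 7.4 is "To determine trough concentrations of BMS-986036 in all participants". Protocol 8.5.5.1 says the concentrations are "derived from trough (predose) blood samples collected from each participant before the administration of BMS-986036 dosing at each visit".

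Protocol 8.1 gives weekly dosing for 48 doses and visits within ±5 days. Section 8.4.2 counts the trough PK sample among the assessments to finish before an in-clinic dose. It also provides for the other case: "If a study visit occurs on a day that is not a planned dosing day", the dose stays on its planned day and "all study-related assessments will continue to be performed at the planned study visit (in-clinic administration of study drug would not occur"). For a missed dose, section 8.4.6.3 has the participant inject as soon as possible and then resume the schedule, provided that "2 doses of medication should not be administered less than 48 hours apart".

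SAP 6.3.1 covers "Trough BMS-986036 serum concentrations (in all participants at all visits"), for both C-terminal intact and Total drug. It reports n, mean, SD, geometric mean, CV, median, minimum and maximum at each scheduled time point, and plots geometric means against scheduled times. Values below the LLOQ are set to missing when means are computed. Under SAP 8.3, an assessment outside its window is a protocol deviation, but "the assessment is recorded in the clinical database at the planned visit". No visible rule refers to the time since the last injection. Text is redacted directly after the quoted part of SAP 6.3.1 and on either side of the off-day sentence in Protocol 8.4.2.

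**The concern.** Under weekly dosing, a trough is the concentration about 168 h after the previous injection. The instruction to hold the dose until blood is drawn secures that timing only when the visit is on the dosing day and the previous dose was on time. Off the dosing day, the sample is taken part-way through the dosing interval yet enters the same row of the trough table as a true predose sample.

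The active analyte falls quickly: Protocol 6.1.2 says it "displayed a half-life of approximately 20 - 24 hours". A few days' difference in sampling time is therefore a multiple of the quantity being reported. What is at stake is the accuracy of the trough table and plots, how stable exposure looks from visit to visit, and any trough-based look at immunogenicity or response. Protocol 6.2.1 lists the PK analyses among the inputs to Phase 3 dose selection.

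**Working it through.** **Inputs.** Dosing interval 168 h and visit window ±5 days (Protocol 8.1 and 8.4.2). For C-terminal intact drug, half-life 20 to 24 h, median time to peak (Tmax) 24 to 33 h, and 2- to 3-fold accumulation on daily dosing (Protocol 6.1.2).

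**Check against the protocol's own figures.** Protocol 8.3.1 equates 5 half-lives with 5 days: 5 × 24 h = 120 h = 5.0 days, which agrees (5 × 20 h = 4.2 days). Accumulation on daily dosing, 1/(1 − 2^(−24/t½)), is 1.8 at 20 h and 2.0 at 24 h. A one-compartment model with first-order absorption, fitted to the stated Tmax, gives trough accumulation of 2.5 to 3.7. The protocol does not say which measure its 2- to 3-fold refers to, and the same model gives 3.8 to 6.0 for AUC, so the agreement is rough.

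**Time since last dose.** A visit e days early is 7 − e days after the last dose. Five days early gives day 2; one day early gives day 6. A visit e days late, with the dose taken on its planned day, is e days after it, so days 1 to 5. Under section 8.4.6.3 a late dose may precede the next planned one by 48 h, so even a dosing-day sample can be at day 2.

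**Ratio to the 7-day trough at weekly steady state**

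- Simple decline: 2^((7 − d) × 24 / t½).
- Absorption model: C(24d)/C(168), where C(t) is the sum over past weekly doses of ka/(ka − k) × (e^(−kt) − e^(−ka·t)), k = ln 2 / t½, and ka is solved from Tmax. At t½ = 20 h the largest Tmax possible without absorption being slower than elimination is 28.9 h, so that value replaces 33 h.

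| Days since dose | t½ 20, Tmax 24 | t½ 20, Tmax 28.9 | t½ 24, Tmax 24 | t½ 24, Tmax 33 | Simple decline (24 h; 20 h) |
|---|---|---|---|---|---|
| 2 | 35.7 | 18.4 | 24.3 | 10.9 | 32; 64 |
| 3 | 20.0 | 12.0 | 14.1 | 7.9 | 16; 28 |
| 4 | 10.1 | 6.9 | 7.6 | 5.1 | 8; 12 |
| 5 | 4.8 | 3.8 | 3.9 | 3.1 | 4.0; 5.3 |
| 6 | 2.2 | 2.0 | 2.0 | 1.8 | 2.0; 2.3 |
| 7 | 1 | 1 | 1 | 1 | 1; 1 |
| 8 | 0.45 | 0.50 | 0.50 | 0.55 | 0.50; 0.43 |

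**Bias in the other direction.** If no dose is missed, dose 48 falls at Week 47. The Week 48 sample is then at day 7, and a visit 5 days late is at day 12 because no further dose is due. Week 52 is 5 × 7 = 35 days after the last dose.

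**Effect on a by-visit summary.** If a share f of samples sits at R times trough and the rest at 1, the arithmetic mean is multiplied by 1 + f(R − 1) and the geometric mean by R^f. The values of f are assumptions.

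| R | f | Arithmetic mean | Geometric mean |
|---|---|---|---|
| 4 | 5% | 1.15 | 1.07 |
| 4 | 10% | 1.30 | 1.15 |
| 4 | 20% | 1.60 | 1.32 |
| 16 | 5% | 1.75 | 1.15 |
| 16 | 10% | 2.50 | 1.32 |
| 16 | 20% | 4.00 | 1.74 |

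The median changes little while off-day samples are a minority.

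**Values below the LLOQ.** A true trough is 168/24 = 7 to 168/20 = 8.4 half-lives after the dose, so values set to missing will tend to be genuine troughs while off-day samples stay in. This adds upward bias to the means. Its size cannot be computed because the LLOQ is not given.

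**The case against.** The strongest reply is that the redactions lie on the disputed point, and that SAP 6.3.1 refers to a PK population whose definition is not visible in SAP 5.0. A timing rule could sit there. This stands as a reason to make the fix conditional. The surrounding text points instead to a separate PK subset: the visible subsection of Protocol 8.5.5 is headed All Participants, and the SAP glossary defines Cmax and Tmax, which trough sampling does not need.

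A reader might infer that the PK objective fails. The documents do not support that. The default is a predose sample on the dosing day, which remains a valid trough. Injection date and time are recorded and all concentrations are listed, so off-day samples can be separated.

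A reader might also infer that the reported troughs will be several-fold too high. That holds for single samples. For the summaries it needs an off-day share that no document gives, and the plotted geometric mean and the median move far less than the arithmetic mean.

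Three further replies stand in part:

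- Week 52/PTFU has its own row in a by-visit table, so it does not contaminate the on-treatment rows; the fault there is the trough label. SAP 6.4 summarises early termination separately for non-biopsy endpoints, but in the exploratory section and without naming PK.
- Off-day sampling has no stated reason to differ between blinded arms, so the expected error largely cancels in dose ratios and mostly adds noise. The LLOQ rule is a possible exception, since it may act differently by dose.
- Exposure-response work is to use model-determined exposures under a separate plan (Protocol 9.5.4). The pooled model behind it is optional, so it does not replace a correct trough table.

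**Conclusion.** The point holds in a limited form. Following the visible text, some samples labelled trough will not be troughs. For C-terminal intact drug such a sample is about 2 times the 7-day value at day 6, 3 to 5 times at day 5, 5 to 10 times at day 4, 8 to 20 times at day 3 and 11 to 36 times at day 2, with higher figures under simple decline. After day 7 it is too low, about half at day 8.

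The by-visit summaries, chiefly the arithmetic mean and SD, can be biased by an amount that cannot be stated without the off-day share. The factors rest on a one-compartment model and on a half-life from obese healthy volunteers. They do not carry over to Total BMS-986036, for which no half-life is given. The PK objective is put at risk but not defeated, and no efficacy analysis is affected. Confidence is limited by the redactions; the sponsor can close the point by confirming that a timing rule exists.

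**What to change.** Unless the redacted text already does this, amend SAP 6.3.1 to:

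- derive actual time since last dose for every PK sample from the recorded injections;
- restrict the by-visit trough table and plots to on-treatment predose samples within a prespecified window around 168 h;
- present Week 52/PTFU as post-treatment concentrations and early termination separately;
- list all other samples with actual time since dose and keep them for the population PK model.

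The window is a choice. At ±24 h it still admits values from about 0.43 to 2.3 times the 7-day trough, so either set it tighter or add a sensitivity summary with a tighter window.

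Nothing changes in visits, dosing or data collection: Protocol 8.4.2 already has injection date and time captured, and SAP 6.5.6.1 lists exposure by injection. The cost is a short SAP edit, one derived variable, and fewer samples per visit in the trough table.
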